Appendix 12. EQ-5D-5L Health Questionnaire

Health Questionnaire

English version for the UK

SAMPLE

UK (English) v.2 © 2009 EuroQol Group. EQ-5D™ is a trade mark of the EuroQol Group

Under each heading, please tick the ONE box that best describes your health TODAY

MOBILITY

- I have no problems in walking about
- I have slight problems in walking about
- I have moderate problems in walking about
- I have severe problems in walking about
- I am unable to walk about

SELF-CARE

- I have no problems washing or dressing myself
- I have slight problems washing or dressing myself
- I have moderate problems washing or dressing myself
- I have severe problems washing or dressing myself
- I am unable to wash or dress myself

USUAL ACTIVITIES (e.g. work, study, housework, family or leisure activities)

- I have no problems doing my usual activities
- I have slight problems doing my usual activities
- I have moderate problems doing my usual activities
- I have severe problems doing my usual activities
- I am unable to do my usual activities

PAIN / DISCOMFORT

- I have no pain or discomfort
- I have slight pain or discomfort
- I have moderate pain or discomfort
- I have severe pain or discomfort
- I have extreme pain or discomfort

ANXIETY / DEPRESSION

[figure not shown]
- I am not anxious or depressed
- I am slightly anxious or depressed
- I am moderately anxious or depressed
- I am severely anxious or depressed
- I am extremely anxious or depressed

- We would like to know how good or bad your health is TODAY.
- This scale is numbered from 0 to 100.
- 100 means the best health you can imagine.
0 means the worst health you can imagine.
- Mark an X on the scale to indicate how your health is TODAY.
- Now, please write the number you marked on the scale in the box below.

YOUR HEALTH TODAY =

SAMPLE

The best health
you can imagine

The worst health
you can imagine

Appendix 13. EORTC QLQ-MY20

EORTC Multiple Myeloma Module (QLQ-MY20)

Patients sometimes report that they have the following symptoms or problems. Please indicate the extent to which you have experienced these symptoms or problems during the past week. Please answer by circling the number that best applies to you.

During the past week:	Not at All	A Little	Quite a Bit	Very Much
31. Have you had bone aches or pain?	1	2	3	4
32. Have you had pain in your back?	1	2	3	4
33. Have you had pain in your hip?	1	2	3	4
34. Have you had pain in your arm or shoulder?	1	2	3	4
35. Have you had pain in your chest?	1	2	3	4
36. If you had pain did it increase with activity?	1	2	3	4
37. Did you feel drowsy?	1	2	3	4
38. Did you feel thirsty?	1	2	3	4
39. Have you felt ill?	1	2	3	4
40. Have you had a dry mouth?	1	2	3	4
41. Have you lost any hair?	1	2	3	4
42. Answer this question only if you lost any hair: Were you upset by the loss of your hair?	1	2	3	4
43. Did you have tingling hands or feet?	1	2	3	4
44. Did you feel restless or agitated?	1	2	3	4
45. Have you had acid indigestion or heartburn?	1	2	3	4
46. Have you had burning or sore eyes?	1	2	3	4

Please turn to next page

During the past week:	Not at All	A Little	Quite a Bit	Very Much
47. Have you felt physically less attractive as a result of your disease or treatment?	1	2	3	4
48. Have you been thinking about your illness?	1	2	3	4
49. Have you been worried about dying?	1	2	3	4
50. Have you worried about your health in the future?	1	2	3	4

Specimen

© Copyright 1999 EORTC Study Group on Quality of Life. All rights reserved.

1 INTRODUCTION

The Study PCYC-1138-CA consisted of a Phase 1 and a Phase 2 part. After completion of the Phase 1 part, in which 11 subjects received study treatment, the sponsor decided to not pursue an indication for treatment of patients with multiple myeloma with ibrutinib and therefore terminate the study early. Thus, this statistical analysis plan (SAP) is to define only the key study elements for the Phase 1 part of the study including variable definitions, and statistical methods for analysis of data in evaluation of efficacy and safety. Analyses of pharmacokinetics data will be addressed in a separate document. Biomarker analysis will not be performed due to early termination of the study. Throughout this SAP, “study treatment” and “study drug” are used interchangeably.

Analysis methods specified in this document take precedence over those described in the study protocol should there be any difference.

1.1 Study Design – Phase 1

The Phase 1 part of the study was an open-label, international, multicenter dose-finding study of the ibrutinib, pomalidomide and dexamethasone combination in subjects with relapsed/refractory multiple myeloma (MM). Up to 18 patients were to be enrolled in order to determine the maximum therapeutic dose/maximum administered dose (MTD/MAD). In the dose finding portion of the study, up to 2 cohorts were to be explored (Table 1). The study followed a 3+3+3 dose escalation design. The MTD/MAD was defined as the highest dose level at which <33% (ie, ≤ 1 of 6 or ≤ 2 of 9) of subjects in a cohort experience a study treatment related dose limiting toxicity (DLT).

Table 1: Dosing Levels and Cohorts

Dose Level	Cohort	Ibrutinib ^a	Pomalidomide ^b	Dexamethasone ^c
-1	-1	420 mg once daily	4 mg	40 mg
1 (Starting Dose)	1	560 mg once daily	4 mg	40 mg
2	2	840 mg once daily	4 mg	40 mg

^a. Ibrutinib was administered PO starting on Day 1 of Cycle 1, dosing was continuous thereafter (without interruption).

^b. Pomalidomide was administered PO on Days 1 – 21 of a 28-day cycle.

^c. Dexamethasone was administered PO once weekly. The dose was reduced to 20 mg weekly in those >75 years of age

1.2 Objective/Endpoints of Study – Phase 1

- **Primary Objective**

- To determine the MTD)/ MAD of the ibrutinib, pomalidomide and dexamethasone combination.
- To determine the safety and tolerability of ibrutinib in combination with pomalidomide and dexamethasone in subjects with relapsed/refractory MM.

- **Secondary Endpoints**

- Overall response rate (ORR): partial response (PR) or better, per the International Myeloma Working Group (IMWG) response criteria (Rajkumar 2011)^{1,2,3}
- Duration of Response (DOR)
- The clinical benefit rate (CBR) and its duration, defined as \geq minimal response (MR) according to the IMWG response criteria
- To evaluate the pharmacokinetics (PK) of ibrutinib and pomalidomide when given in combination with dexamethasone

1.3 Sample Size Determination

Phase 1: This was a standard 3+3+3 design to determine the MTD/MAD and toxicity profile of ibrutinib in combination with pomalidomide and dexamethasone. Dose escalation were to follow the 3+3+3 principle and up to 2 cohorts were to be explored. This study was not powered for comparison of treatment cohorts. Up to 18 subjects were to be enrolled into the Phase 1 part of the study.

1.4 Planned Analysis

- **Final Analysis**

The final analysis for the clinical study report will be conducted when all Phase 1 subjects have exited PCYC-1138-CA study. The sponsor decided not to perform the Phase 2 part of the study following a decision not to pursue an indication for multiple myeloma for ibrutinib.

2 GENERAL ANALYSIS CONSIDERATION

Subjects will be analyzed and summarized for safety and other selected endpoints.

2.1 Analysis Sets

- **Safety Population**

The safety population include subjects who have received any dose of study treatment.

- **Response-Evaluable Population**

The response-evaluable population is defined as subjects who are in safety population and provided at least one post-baseline response (or disease) assessment. All subjects in safety population received at least 1 post-baseline response assessment.

3 SUBJECT INFORMATION

3.1 Subject Disposition

The disposition tables will include the following summaries.

- Analysis population
- Study Treatment Disposition and Discontinuation
- Study Status, Duration of Treatment and Study Exit

Time on study is defined as the interval between the date of first dose and the date of last known to have been alive. The Kaplan-Meier method will be used to estimate the median time on study with subjects who died being censored at death date.

3.2 Demographics and Baseline Characteristics

Subject demographics, baseline characteristics and baseline disease characteristics will be summarized with descriptive statistics for the safety population.

3.3 Concomitant Medications

Medications will be coded to Anatomical Therapeutic Chemical (ATC) class and the preferred drug name (hereafter referred as “preferred name”) per World Health Organization drug dictionary. Listings will be provided to present the data.

Concomitant CYP3A inhibitors and inducers taken any time while on study treatment (i.e., from the date of first dose through the date of last dose of the study treatment) will be summarized by ATC class and preferred term (PT). Each subject will be counted once for each PT, and each ATC class.

3.4 Extent of Exposure to Study Treatment

Exposure to the 3 study drugs will be summarized for the safety population. Descriptive statistics will be provided for the following data for each of the 3 drugs unless otherwise specified: treatment duration (month) and number (%) of subjects with dose reduction due to adverse events (AEs).

4 ANALYSIS FOR ENDPOINTS

Analysis of secondary endpoints (Table 2) will be conducted on the safety population.

Table 2: Definitions and Analyses for Secondary Endpoints

Endpoint	Definition	Analysis Method
Secondary endpoints:		
Overall Response Rate (ORR)	The proportion of subjects achieving a best overall response of PR or better per investigator assessment per IMWG at or prior to initiation of subsequent anticancer therapy	ORR will be estimated and the corresponding 2-sided 95% exact binomial confidence interval will be calculated.
Duration of Response (DOR)	The time interval between the date of initial documentation of a response and the date of first documented evidence of PD, death, or date of censoring for the subjects not progressed/died. The censoring date is the last adequate tumor assessment date.	A listing will be provided.
Clinical Benefit Rate (CBR)	The proportion of subjects achieving a best overall response of MR or better per investigator assessment per IMWG at or prior to initiation of subsequent anticancer therapy	CBR will be estimated and the corresponding 2-sided 95% exact binomial confidence interval will be calculated.

Note: DOR; duration of response; PD: disease progression; PR: partial response; MR: minimal response; IMWG: International Myeloma Working Group.

5 SAFETY ASSESSMENTS

Safety data will be summarized for safety population unless otherwise indicated. Table 3 summarizes the safety analyses to be carried out. AEs will be coded in accordance with the Medical Dictionary for Regulatory Activities (MedDRA). Severity of AEs were graded by the investigator according to the NCI Common Terminology Criteria for Adverse Events (NCI-CTCAE) v4.03. A listing will be provided to indicate dose-limiting toxicity (DLT).

In general, the treatment-emergent period is defined as the period from the date of the first dose of study treatment up to 30 days after the date of the last dose of study treatment or the day before initiation of subsequent anticancer therapy, whichever comes first. Treatment emergent AEs are those events that occur or worsen during the treatment-emergent period or that are related to the study treatment or events with a complete missing onset date but with a resolution date during the treatment phase.

All laboratory values will be converted to and reported as international standard (SI) units. In general, only data from the central laboratory will be summarized and analyzed. Laboratory parameters will be graded using the NCI CTCAE v4.03.

Table 3: Summary of Safety Assessments

Assessment Type	Definition	Analysis Methods
AE	TEAEs, SAEs, non-serious TEAE, grade 3 or worse TEAEs, related TEAEs, TEAEs leading to treatment discontinuation, TEAEs leading to dose reduction, TEAEs leading to death, protocol- defined events of special interest and other safety observations	Descriptive summary statistics and/or listings
Lab	Worst post-baseline toxicity grade for selected CTCAE gradable hematology and chemistry. Abnormalities in creatinine clearance, uric acid, and liver function	Descriptive summary statistics and/or listings
Vital Signs and other Observations Related to Safety	SBP, DBP, weight, heart rate, new or worsened eye-related symptoms	Descriptive summary statistics and/or listings
Dose Limiting Toxicity (DLT)	DLT	Listing

TEAE: treatment-emergent adverse event; SAE= serious adverse event; SBP: systolic blood pressure; DBP: diastolic blood pressure; CTCAE= Common Terminology Criteria for Adverse Events.

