The Screening Phase assessments will be performed within 28 days prior to study treatment. Eligible subjects will have relapsed/refractory MM, having received at least 2 prior therapies including lenalidomide (LEN) and either bortezomib or carfilzomib, and have demonstrated disease progression on or within 60 days of completion of most recent treatment regimen ([Rajkumar 2011](#)). Subjects who satisfy all the inclusion/exclusion criteria are eligible to enter the study.

The Treatment Phase will extend from first dose of study treatment for Phase 1 and randomization (Arm A and Arm B) or enrollment (Arm C) for Phase 2b until the End-of-Treatment (EOT) visit (which should occur 30 days from last dose of study drug or prior to the start of a new anti-cancer treatment). Initiation of study treatment should occur within 28 days of consenting and Screening procedures, following approval by the Sponsor's medical monitor for Phase 1 and 3 days of randomization/enrollment for Phase 2b. Subjects enrolled in Phase 1 will receive ibrutinib in combination with pomalidomide and dexamethasone according to [Section 5.1](#). Subjects in Arms A and B of Phase 2b will receive pomalidomide and dexamethasone per protocol design. In addition, all subjects in Arms A and B, according to randomization, will receive oral study drug (ibrutinib or matching placebo), administered continuously. Subjects in Arm C will receive the combination of pomalidomide and dexamethasone per protocol design with oral ibrutinib administered daily. All subjects will continue study treatment until criteria for permanent discontinuation of study drug are met ([Section 5.8](#)), such as disease progression (confirmed by IRC for Phase 2b), study drug is no longer tolerated by subject, or study end. Further information on dosing is provided in [Section 5](#). Efficacy evaluations will be performed as specified in [Section 7.5](#). Subjects with progressive disease (confirmed by IRC for Phase 2b) must discontinue all study treatment. The Post-treatment Follow-up Phase will begin once a subject discontinues study treatment and will continue until death, lost to follow up, consent withdrawal, or study end, whichever occurs first.

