The verbatim terms used in the eCRF by Investigators to identify AEs will be coded using the Medical Dictionary for Regulatory Activities (MedDRA) and graded according to [NCI CTCAE version 4.03](#). Treatment-emergent adverse events are those AEs occurring after the first dose of study treatment and within 30 days following the last dose of study treatment (ibrutinib, pomalidomide, or dexamethasone, whichever occurs later), but before first dose date of subsequent anti-cancer therapy, whichever occurs first; any AE that is considered study drug-related regardless of the start date of the event; or any AE that is present at baseline but worsens after the first administration of study treatment in severity or is subsequently considered drug-related by the Investigator.

All TEAEs will be included in the analysis. The number and percent of subjects with TEAEs will be summarized by system organ class and preferred term. Drug related AEs, SAEs, Grade ≥ 3 AEs, AEs leading to study treatment discontinuation, dose modification, or death, and events of special interest will be summarized and listed.

Clinical Laboratory Tests

Laboratory tests will be summarized separately for hematology and serum chemistry. All laboratory values will be graded using the [NCI CTCAE \(version 4.03\)](#). The worst toxicity grade during the study will be tabulated.

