11.2.2. Adverse Event Reporting Procedures

11.2.2.1. All Adverse Events

All subjects who receive at least one dose of study drug(s) will be considered evaluable for safety assessments. All AEs whether serious or non-serious, will be documented from the time signed and dated ICF is obtained until 30 days following the last dose of study drug. All SAEs will be reported to the Sponsor Drug Safety via an SAE reporting form and will be recorded in

the eCRF from the time of ICF signing. Non-serious AEs will be recorded in the source documents from the time of ICF signing and will be recorded in the eCRF from the first dose of study drug(s).

Serious adverse events occurring more than 30 days following the last dose of study drug should also be reported if considered related to any of the study drugs. Resolution information after 30 days should be provided.

Progressive disease should NOT be reported as an AE, but instead symptoms/clinical signs of disease progression may be reported (See [Section 11.1.1](#)).

All AEs, regardless of seriousness, severity, or presumed relationship to study drug, must be recorded using medical terminology in the source document. All records will need to capture the details of the duration and the severity of each episode, the action taken with respect to the study drug, Investigator's evaluation of its relationship to the study drug, and the event outcome. Whenever possible, diagnoses should be given when signs and symptoms are due to a common etiology (e.g., cough, runny nose, sneezing, sore throat, and head congestion should be reported as "upper respiratory infection"). Investigators must record in the eCRF their opinion concerning the relationship of the AE to study therapy. All measures required for AE management must be recorded in the source document and reported according to Sponsor instructions.

All deaths should be reported with the primary cause of death as the AE term, as death is typically the outcome of the event, not the event itself. Autopsy and postmortem reports must be forwarded to the Sponsor, or designee, as outlined above, if allowed per local regulatory guidelines.

If a death occurs within 30 days after the last dose of study drug, the death must be reported to the Sponsor as a SAE.

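### Read literally, the SAP leaves an unrelated adverse event with no onset date out of the TEAE summaries when it is ongoing or resolves after the treatment phase

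*SAP*

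**What the plan says.** SAP section 5 first sets a treatment-emergent period, which runs "from the date of the first dose of study treatment up to 30 days after the date of the last dose of study treatment" or to the day before subsequent anticancer therapy, whichever is earlier. It then defines the TEAE. Two limbs come first: "Treatment emergent AEs are those events that occur or worsen during the treatment-emergent period or that are related to the study treatment". A third limb adds "events with a complete missing onset date but with a resolution date during the treatment phase". That third limb is the only rule for missing onset dates in either document, and the SAP has no date imputation rule.

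The third limb refers to the treatment phase, not to the period just defined, and the SAP does not say what the treatment phase is. Protocol section 3 does: in Phase 1 it runs from first dose "until the End-of-Treatment (EOT) visit (which should occur 30 days from last dose of study drug", or before new anti-cancer treatment.

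Protocol section 10.6 defines TEAEs as "those AEs occurring after the first dose of study treatment and within 30 days following the last dose" of study treatment, and adds, among other routes, "any AE that is considered study drug-related regardless of the start date of the event". It is silent on missing dates. SAP section 1 says that the SAP's methods prevail where the two documents differ.

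Table 3 of the SAP lists the adverse event summaries, beginning "TEAEs, SAEs, non-serious TEAE, grade 3 or worse TEAEs, related TEAEs". Most depend on the TEAE flag. SAEs are named without it, and dose-limiting toxicities have their own listing.

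**The concern.** When the onset date is completely missing, an end date before first dose is what shows that an event was over before treatment. The SAP does not use that test. It asks for an end date inside the treatment phase, so an event with no end date fails, although it may have started on treatment. Of two unrelated events that both lack an onset date, the one that resolved in the treatment phase counts and the one that is still ongoing does not.

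Safety and tolerability is a primary Phase 1 objective (Protocol section 2.1, SAP section 1.2), and the TEAE flag feeds most of the adverse event summaries that address it. With few subjects, one misclassified event is visible in a table of percentages.

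**Working it through.** No sample size or error rate is involved. The check applies the SAP's three limbs, case by case, to an event whose onset date is completely missing, and then applies the proposed rule.

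**Inputs.** Limb 1: occurs or worsens in the treatment-emergent period. Limb 2: related. Limb 3: no onset date, but resolved in the treatment phase (all SAP section 5). Treated subjects: 11 (SAP section 1).

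| Event with no onset date | SAP as written | Proposed rule |
|---|---|---|
| Related | TEAE, limb 2 | TEAE |
| Unrelated, worsening documented in the period | TEAE, limb 1 | TEAE |
| Unrelated, resolved in the treatment phase | TEAE, limb 3 | TEAE |
| Unrelated, ongoing | Not a TEAE: no resolution date for limb 3, and limb 1 cannot be shown without an onset date | TEAE, unless shown to have begun after the period |
| Unrelated, resolved after the treatment phase | Not a TEAE, for the same reason on limb 1; limb 3 fails on the date | TEAE, unless shown to have begun after the period |
| Unrelated, resolved before first dose | Not a TEAE | Not a TEAE |

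The fourth and fifth rows, without documented worsening, are the gap.

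**Where the treatment phase ends.** The End-of-Treatment visit is due 30 days after last dose with a window of 7 days either way (Protocol section 8.3.12), so it falls between 30 − 7 = 23 and 30 + 7 = 37 days after last dose. The treatment-emergent period ends at 30 days, so on the section 3 definition the two windows nearly coincide. Some protocol text points elsewhere. Section 3 also starts post-treatment follow-up once study treatment is discontinued, and section 5.4.4 ends the Treatment Phase when ibrutinib is stopped for toxicity. Section 8.4, however, starts follow-up only after the End-of-Treatment visit. The explicit definition is the one in section 3, but the SAP does not cite it.

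**Size.** Removing one subject from a TEAE row of an all-subject table moves that row by 1/11 = 0.0909, or 9.1 percentage points, and only if the subject has no other qualifying event in the row. The protocol synopsis says that Phase 1 adverse events are also summarized by dose cohort. The cohort split of the 11 is not given. If a cohort holds 3 to 9 subjects (Protocol section 5.1), one subject is 1/9 = 11.1 to 1/3 = 33.3 points of that cohort's column. Neither document says how many onset dates are completely missing; the number may be zero.

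**The case against.** The strongest reply is that data collection already settles the matter. Adverse events between consent and first dose go to medical history (Protocol section 7.1.6), and non-serious events enter the eCRF only from first dose, with routine collection ending 30 days after last dose (section 11.2.2.1). A non-serious event on the adverse event form should therefore lie in about the treatment-emergent window and meet limb 1 whatever its dates. Section 11.2.2.1 also asks for the duration of each episode, which should make a missing onset rare. This stands as a reason to expect little effect. It does not close the gap: the SAP does not say that a recorded event is presumed to have begun on treatment, and if it did, limb 3 would be largely redundant. If nearly all recorded non-serious events began after first dose, leaving one out for lack of an end date is harder to defend.

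Several stronger readings are tempting, and the documents do not support them:

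- A reader might infer that events resolving in the 30 days after last dose are lost. On the Protocol section 3 definition nearly all of them fall inside the treatment phase. What remains is an undefined term.
- A reader might infer that the clause lowers TEAE counts. It is an added limb, so beside the other two it can only bring events in, and the protocol has no such provision. Counts are lower only in comparison with the rule proposed here.
- A reader might infer that these events vanish from all safety output. A serious event can still appear in the SAE summary, and a dose-limiting toxicity in its listing.
- A reader might infer that the longest-lasting events are systematically removed. The documents give no data on durations or on missing dates.

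A replacement rule with no upper limit would also be wrong. New malignancies are reportable regardless of cause up to 5 years after last treatment (Protocol section 11.2.3), so a late, unrelated one with no onset date would become a TEAE.

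**Conclusion.** The point holds as a narrow one. An adverse event with a completely missing onset date is left out of the TEAE-based summaries if it is unrelated, has no documented worsening in the treatment-emergent period, and is ongoing or resolved after the treatment phase. It may nevertheless have started on treatment. This rests on a literal reading of SAP section 5 and on the protocol's definition of the Treatment Phase.

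The expected effect is small: 11 treated subjects, descriptive summaries, an unknown and probably low number of missing onset dates, and at most 9.1 percentage points per affected subject in an all-subject row. It is an inexpensive improvement and does not threaten the study's conclusions.

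**What to change.** Replace the third limb with: 'An event with a completely missing onset date is treatment-emergent unless its resolution date is before the first dose of study treatment, or other recorded information (such as the first report date) shows that it began after the treatment-emergent period.'

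The first condition keeps out events that were over before treatment. The second keeps out late events such as an unrelated malignancy reported in long-term follow-up. The wording also removes the undefined term, so nobody has to decide where the treatment phase ends.

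The cost is one sentence in the SAP, a small change to the TEAE derivation, and a look at any event that relies on the second condition. The downside is that a pre-treatment event could occasionally be counted. The likeliest source is a serious event, because SAEs are recorded in the eCRF from consent (Protocol section 11.2.2.1).
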